## 6. Statistical Analysis

**Statistical Considerations and Power:** Existing data of monthly onset-to-hospital arrival times and EMS utilization from January 2013 to December 2017 (five years; n=60 months) will be obtained through AHA. We will assume approximately one-third (20 months) will be post-intervention periods. The effect size will be defined as the sum of expected slope change (i.e. monthly change) over the standard deviation. Table 1 shows the study power by autocorrelation level and effect size. Assuming pre-intervention EMS use rate is 50% on average (SD: 3%; 40 months of data) and post-intervention EMS use rate is 55% on average (SD: 3%; 20 months of data; auto-correlation=0.3) and no trend change (“flat”) in pre- or post-intervention periods, this 5% step-increase will be significant at 90% power at a significance level of 0.05. For a 10% step-increase (the goal) with the same assumptions, power is nearly 100%.

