### **Specific Aim 3 (Comparative Effectiveness-Behavior and Action)**

To compare the effectiveness of these interventions on behavior or action, we will monitor early hospital arrival and EMS use for stroke over a 60-month period at the 2 intervention hospitals using an interrupted time-series analysis. Early hospital arrival will be defined as the proportion of stroke patients arriving within 3 hours from symptom onset while EMS utilization (%) will be defined as the proportion of stroke patients arriving to the emergency department by EMS. Segmented regression analysis will be conducted to estimate whether and how much the intervention changes EMS utilization in each of the 2 target hospitals and in aggregate at both hospitals. Autoregressive error will account for correlations of the data across time points. In secondary analyses, temporal trends in early hospital arrival and EMS utilization from 2 pre-selected non-intervention Chicago hospitals (St. Elizabeth and Swedish Covenant) and from hospitals in St. Louis, a comparable Midwestern city, will be compared with the 2 intervention neighborhoods/hospitals in Chicago.

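### The Aim 3 segmented regression has no seasonal term; a yearly cycle, if there is one, can bias the level change, and one annual sine/cosine pair is cheap protection

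*Combined protocol and SAP*

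**What the plan says.** Section 4, Specific Aim 3 (Behavior and Action), gives the model: "Segmented regression analysis will be conducted to estimate whether and how much the intervention changes EMS utilization", at each of the two hospitals and in aggregate. On dependence it adds: "Autoregressive error will account for correlations of the data across time points". The order of the autoregression is not stated. Non-intervention hospitals in Chicago and hospitals in St. Louis are compared only in secondary analyses.

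Section 6 (Statistical Analysis) sets the series as monthly values "from January 2013 to December 2017 (five years; n=60 months") and the split as "We will assume approximately one-third (20 months) will be post-intervention periods". The planning input for the months before the break reads "Assuming pre-intervention EMS use rate is 50% on average (SD: 3%; 40 months of data"). For the months after the break, the same sentence of the power paragraph takes "post-intervention EMS use rate is 55% on average (SD: 3%; 20 months of data; auto-correlation=0.3"). Flat trends are assumed in both periods.

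Neither section mentions season, calendar month or harmonic terms, and nor do the Aim 3 limitations in section 7. No seasonal amplitude is given for EMS use or early arrival.

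**The concern.** The level change at the break is central to what Aim 3 estimates. A yearly cycle is a pattern in the mean. An autoregressive error changes the weights and the standard error but puts no cycle into the fitted mean. With no seasonal term, part of any cycle can therefore be absorbed by the level-change coefficient. How much depends on where the break falls in the cycle and on how far the cycle overlaps with the trend and slope terms. The main analysis at the two intervention hospitals has no concurrent comparator, so a cycle shared with other hospitals is not differenced out of it. If a cycle exists, a seasonal swing could be read as an intervention effect or could hide one.

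**Working it through.** **Inputs from the plan (section 6).** 60 months, about 40 before and 20 after the break; SD 3 percentage points; autocorrelation 0.3; a 5-point step; significance level 0.05.

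**Assumptions.** Break after month 40; AR(1) errors; two-sided test; slope change coded from the first post-intervention month. The documents fix none of these.

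**1. The plan's own power figure.** Let X be the design matrix and V the AR(1) covariance. The generalised least squares (GLS) variance is C = (X′V⁻¹X)⁻¹, SE is the root of the level-change entry, and power = Φ(5/SE − 1.96). The plan states "this 5% step-increase will be significant at 90% power at a significance level of 0.05". I get 99.6% (step only), 78.8% (common trend) and 70.0% (level plus slope; SE 2.012, so Φ(2.485 − 1.96) = Φ(0.525)). None reproduces 90%. The method behind that figure is not described, and it is a separate matter from this point. The statement "For a 10% step-increase (the goal) with the same assumptions, power is nearly 100" percent does reproduce: in the level-plus-slope model, Φ(10/2.012 − 1.96) = Φ(3.01) = 99.9%.

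**2. Bias per point of amplitude.** Let h be the row of C X′V⁻¹ for the level change. A cycle A·cos(2π(t − m)/12) shifts the estimate by A·h′cos(2π(t − m)/12). The maximum over the peak month m is A·√[(h′cos(2πt/12))² + (h′sin(2πt/12))²]. With autocorrelation 0.3:

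| Break after month | Step only | Common trend | Level plus slope | SE ratio with one pair (level plus slope) |
|---|---|---|---|---|
| 36 | 0.015 | 0.667 | 0.750 | 1.038 |
| 38 | 0.139 | 0.543 | 0.712 | 1.033 |
| 40 | 0.257 | 0.368 | 0.543 | 1.018 |
| 42 | 0.319 | 0.328 | 0.351 | 1.007 |
| 48 | 0.030 | 0.386 | 0.982 | 1.052 |

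**3. What drives it.** At 40/20, January to April occur four times before the break and once after; May to December occur three times and twice. That imbalance explains the step-only figure, which almost vanishes with whole years (0.015 at 36/24, 0.030 at 48/12). The level-plus-slope figure rises with whole years (0.750 and 0.982), so month balance is not the cause there.

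**4. Dependence on phase.** In the level-plus-slope model at 40/20, the bias per point is −0.527 for a January peak, −0.151 for March, +0.130 for April and +0.527 for July. It passes through zero between March and April, and again between September (+0.151) and October (−0.130).

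**5. Plausible amplitude.** A cycle of amplitude A has variance A²/2 and lag-1 autocorrelation cos(30°) = 0.866. Suppose SD 3 (variance 9) is the total monthly variation and the residual autocorrelation is not negative. Then (A²/2)(0.866)/9 ≤ 0.3, so A ≤ √(2 × 2.7/0.866) = 2.5. Over A = 1 to 2.5, the worst-phase level-plus-slope bias is 0.543 × 1 = 0.54 to 0.543 × 2.5 = 1.36 points.

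**6. Effect on the test.** With d = bias/SE, type I error = Φ(−1.96 + d) + Φ(−1.96 − d). Keeping SE at 2.012, A = 1 gives d = 0.27 and 5.8%; A = 2 gives d = 0.54 and 8.4%; A = 2.5 gives d = 0.67 and 10.4%. All are worst-phase values.

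**7. After adding one sine/cosine pair (40/20).** The bias from a 12-month sinusoid is zero. The SE rises by 1.4% (step only), 1.0% (common trend) and 1.8% (level plus slope, 2.012 to 2.047). In the last model, power for 5 points moves from 70.0% to 68.5%. Two pairs cost 2.3% and eleven month indicators 4.1%.

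**8. Limit of one pair.** A 1-point rise confined to February to April biases the level-plus-slope estimate by −0.31 without a seasonal term and still by −0.26 with one pair. For December to February the figures are −0.14 and +0.10.

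**The case against.** The strongest case against is that nothing in the documents shows that EMS use or early arrival is seasonal as a proportion of stroke patients, so a seasonal term is optional. That stands, and it keeps this point conditional.

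The break date is also an assumption. Section 6 says only approximately one-third, and Aim 2 spreads promoter training over six months. That stands too, which is why a range of breaks is shown.

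Noise may swamp the effect. Section 5 gives 413 + 353 = 766 admissions in 2013, or about 64 a month. At 50% EMS use, the binomial SD alone is √(0.25/63.8) = 6.3 points. With SD 6 the SE doubles to about 4.0, and a 2-point cycle at its worst phase gives a type I error of only 5.8%. That is correct for the test, but the bias in points is unchanged. The 2.5-point ceiling on amplitude also depends on SD 3, so a larger SD would loosen it.

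Finally, the control hospitals could reveal or offset a shared cycle, but only in the secondary comparison.

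Three stronger readings are tempting and not supported. A reader might infer that unequal calendar coverage is the cause and that balancing the months is the cure; in the level-plus-slope model, whole-year splits are worse. A reader might infer that bias could exceed 2 points by assuming a 4-point cycle; such a cycle has variance 8 of the plan's 9 and a lag-1 autocorrelation of about (8/9)(0.866) = 0.77, which conflicts with SD 3 and 0.3. A reader might also infer that one pair removes any seasonal pattern; it removes only a sinusoid.

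**Conclusion.** The point holds as a cheap improvement, not as a demonstrated flaw in the result. The main segmented model leaves the level change exposed to any yearly cycle, and neither the autoregressive error nor the secondary comparisons protect that estimate. The bias ceiling in the level-plus-slope model is about 0.5 to 1.4 points, roughly a tenth to a quarter of the planned 5-point step. It rests on a 40/20 split, AR(1) at 0.3, an assumed amplitude of 1 to 2.5 points and the worst phase. The direction depends on the unknown phase, and the true bias may be near zero. The documents neither show a cycle nor rule one out.

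**What to change.** In Specific Aim 3, state that the segmented regression for both EMS use and early arrival includes one annual sine/cosine pair. Name calendar-month indicators, or a second harmonic pair, as a sensitivity analysis for a cycle that is not sinusoidal. Fixing this in advance also avoids choosing a seasonal form after the level change has been seen.

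The change is one or two clauses of text. It uses two degrees of freedom and enlarges the standard error by about 1 to 2% at 40/20; in the level-plus-slope model the cost runs from 0.7% to 5.2% for breaks between months 36 and 48. If the SD of 3 already contains a cycle, the pair also lowers the residual variance and the net cost is smaller. If there is no yearly cycle, there is no gain.

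### The effect size is defined on slope change but the example powers a level step, and the stated 90% is not supported for the level-plus-slope model that the definition points to

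*Combined protocol and SAP*

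**What the plan says.** The power paragraph of the Statistical Analysis section fixes the effect size first: "The effect size will be defined as the sum of expected slope change (i.e. monthly change) over the standard deviation". It continues: "Table 1 shows the study power by autocorrelation level and effect size".

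The worked example uses other terms. EMS use averages 50% (SD 3%) over 40 pre-intervention months. After that, "post-intervention EMS use rate is 55% on average (SD: 3%; 20 months of data; auto-correlation=0.3". The trend assumption is "no trend change (“flat”) in pre- or post-intervention periods". The conclusions are that "this 5% step-increase will be significant at 90% power at a significance level of 0.05" and, for the larger effect, "For a 10% step-increase (the goal) with the same assumptions, power is nearly 100" per cent.

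The analysis itself is described under Specific Aim 3 (Behavior and Action): "Segmented regression analysis will be conducted to estimate whether and how much the intervention changes EMS utilization", and "Autoregressive error will account for correlations of the data across time points". No regression terms, tested coefficient, autoregressive order or sidedness are given there or in the Statistical Analysis section.

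The Limitations text for Aim 3 adds that a 5% change in EMS use is detectable with more than 80% power, unless admissions fall.

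**The concern.** The definition and the example concern different parameters. A change in monthly slope and a change in level are separate coefficients in a segmented regression. Their standard errors differ, and so does their power. A reader cannot tell which coefficient the 90% refers to, or place the example on a table indexed by a slope-based effect size.

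This matters because the power for a 5-point step depends heavily on which terms are fitted. An effect size built on slope change suggests a model that contains a slope-change term. In such a model the step is estimated much less precisely than in a step-only comparison. If that is the model, the 90% and the Limitations figure are both too favourable, and a null result for EMS use could be read as stronger evidence against a 5-point effect than it is. With the tested coefficient left open, it could also be chosen after the data are seen.

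**Working it through.** **Definition against example.** Flat series before and after mean that the slope change is 0. The definition as worded then gives 0/3 = 0. The effect that is powered is (55 − 50)/3 = 1.67 SD.

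**Inputs from the Statistical Analysis section.** 60 months, break after month 40, SD 3 points, autocorrelation 0.3, steps of 5 and 10 points, alpha 0.05.

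**Assumptions not in the plan.** AR(1) errors, SD 3 as the marginal SD, the model terms listed below, and a two-sided test (one-sided also shown).

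**Method.** The error covariance is V = 9 × 0.3^|i−j|. The standard error (SE) of the step is the square root of its diagonal element in (X′V⁻¹X)⁻¹. Power comes from the noncentral t distribution with noncentrality step/SE and 60 − p degrees of freedom, where p is the number of regression terms including the intercept.

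**What the plan's 90% requires.** In the normal approximation, SE = 5/(1.960 + 1.282) = 1.54.

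| Terms fitted | SE of step | Step/SE at 5 points | Power, two-sided | Power, one-sided |
|---|---|---|---|---|
| Step only | 1.086 | 4.61 | 99.5% | 99.8% |
| Common trend + step | 1.812 | 2.76 | 77.4% | 86.0% |
| Level + slope change, post-time from 0 | 2.012 | 2.49 | 68.5% | 79.1% |
| Level + slope change, post-time from 1 | 2.087 | 2.40 | 65.4% | 76.5% |
| Flat pre, fitted post-slope, post-time from 0 | 1.746 | 2.86 | 80.4% | 88.2% |
| Flat pre, fitted post-slope, post-time from 1 | 1.864 | 2.68 | 75.1% | 84.3% |
| Fitted pre-slope, flat post, step read at month 40 | 1.488 | 3.36 | 91.0% | 95.3% |
| Fitted pre-slope, flat post, step read at month 41 | 1.525 | 3.28 | 89.7% | 94.5% |

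Only the last pair comes close to the required SE of 1.54 and gives about 90% two-sided. A joint two-degree-of-freedom test of level and slope change gives 66.9%.

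**Meaning of the SD.** If 3 is the innovation SD, the marginal SD is 3/√(1 − 0.09) = 3.14. Two-sided power at 5 points is then 61-64% (level + slope change), 73.5% (common trend + step) and 99.1% (step only).

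**Ten-point step at SD 3.** The lowest two-sided figure is 99.7%, in the level-plus-slope model with post-time from 1. The plan's statement reproduces.

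**Plausibility of SD 3.** The table in the Study Participants section gives 413 + 353 = 766 admissions a year at the two intervention hospitals, or 766/12 = 63.8 a month. Binomial noise alone at 50% is √(0.5 × 0.5/63.8) = 0.063, about 6 points for the two hospitals combined. The step-only SE would then be 1.086 × 6.2/3 = 2.24, and 5-point power about 59%.

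**The case against.** The strongest reply is that no miscalculation has been shown. The plan does not list its model terms, and the models above span 65% to 99.5% two-sided, so 90% lies inside the range. One of them, a fitted pre-slope with a flat post period, gives 90% almost exactly. This part of the reply stands. A reader might infer that the 90% is an arithmetic error, or that fitting any trend makes it too high. The documents support neither reading. Holding the pre period flat and fitting a post-slope can even just meet the 80% in the Limitations text (75.1% to 80.4%, depending on time coding), and a step-only model makes 90% conservative.

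A second reply is that the definition has simply lost a term: a sum with one summand looks incomplete, and with a level term restored the example gives (5 + 0)/3 = 1.67. The sentence may also serve only Table 1, whose body is not in the text available here; that absence is no fault of the plan. This too is plausible, but the sentence then still needs repair.

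A third reply is that 90% and more than 80% do not conflict with each other. That is correct. The question is whether the planned model delivers either.

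The replies do not remove the main difficulty. The only pointer to the model in the power paragraph is an effect size based on slope change. With level and slope change both fitted, neither 90% nor 80% is reached, one-sided or two-sided.

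**Conclusion.** The concern holds in a limited form. The effect-size definition does not fit the worked example. The 90% for a 5-point step is unsupported for the model which that definition points to: there the power is about 65-69% two-sided (77-79% one-sided), so a true 5-point step would be missed about one time in three. With a common trend plus step it is 77% (86% one-sided).

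The link from the slope-based effect size to a model with both terms is an inference; the plan does not state it. The figures rest on AR(1) errors and a marginal SD of 3.

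A reader might go further and call Aim 3 underpowered. That does not follow from this point: at SD 3 the 10-point goal keeps 99.7% power or more in every model tried. Whether SD 3 is realistic is a separate question, and all the power figures at SD 3 depend on it.

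**What to change.** In the Statistical Analysis section:

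- Define the effect size on the parameter to be tested. For a step this is level change over SD, 1.67 in the example.
- List the regression terms and the tested coefficient, and state the autoregressive order, the sidedness, and whether the SD of 3 is marginal or innovation.
- Check that SD against monthly volume before any new figure is inserted.
- Recompute and restate the 5-point power for the chosen model. At SD 3, two-sided, this is about 65-69% with level and slope change, 77% with a common trend plus step, or 99.5% with a step only.
- Bring the more-than-80% statement in the Limitations text into line, and check that Table 1 uses the same definition.

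The cost is recalculation and rewording, with no change to data or design. The downside is that the stated 5-point power becomes less favourable if level and slope change are both fitted. At SD 3 the 10-point statement can stay.

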## 7. Anticipated Results and Potential Problems

### Importance of the Knowledge to be Gained

The goal of this study is to develop a better understanding of individual- and community-level barriers to stroke awareness and action. The study addresses an important gap in our current ability to improve stroke outcomes. The study results will advance our knowledge of barriers to calling 911 after stroke and help develop solutions to overcome them in urban multi-ethnic communities. Subsequent adoption by other cities and non-urban populations is likely as the methodology could be replicated elsewhere and potentially for other emergency conditions like heart attack and cardiac arrest. By addressing methodological issues, a culturally specific innovative education program targeted for the minority communities can be successfully implemented. This study also can provide valuable insights on within group and between group variability in the barriers for

accessing stroke care. These may be relevant for future applications, refinement, and iterations of the intervention.

### **Limitations and Alternatives**

**Aim 1:** Focus groups are time consuming and resource intensive. The outcome of the focus groups will reflect small sample sizes compared to the amount of data that quantitative surveys are able to collect. Focus groups may become influenced by one or two dominant people, which may bias the output since other respondents may feel pressure to answer questions in a similar manner to the overriding voices. If the moderator phrases the questions differently between groups they may bias the findings. In addition, focus groups are conducted in an artificial environment which could influence the responses. An alternative to the focus group would be to conduct additional in-depth interviews. If we notice diverse opinions are not shared and individuals are not heard, we could follow-up with them individually.

**Aim 2:** Because the MIP-PACT program will attempt to disseminate information to a broad audience in diverse settings, it may be difficult to retain control over all aspects of the dissemination process. Stroke Promoters may modify the content and format of the original program, making it difficult to evaluate the results of their efforts and avoid heterogeneity.

**Aim 3:** There is potential that our 2 intervention hospitals, which admitted nearly 800 stroke patients in 2013, will have a decrease in stroke admissions. However, barring this unlikely scenario, we will be able to detect a 5% change in EMS utilization with >80% power. Since data are entered by participating sites into a web-based registry without central adjudication or oversight, there remains a possibility of data entry error or incomplete data entry. Clinical data from the GWTG-Stroke registry have been found to be associated with > 95% accuracy on a recently completed national audit (Xian 2012).
